12.0 Statistical Considerations

12.1 To estimate the rates of local failure and tumor progression

The primary objective is to estimate the local control and patterns of failure for patients with primary musculoskeletal tumors including the Ewing's sarcoma family of tumors (ESFT), rhabdomyosarcoma (RMS) and non-rhabdomyosarcoma soft tissue sarcoma (STS) treated with image guided three-dimensional conformal radiation therapy. Different tumor types are accessioned to this study and their local failure rates differ significantly. To account for these differences, three groups of patients will be selected for local failure analysis based on the expected accrual of these patients to this study (Appendix E). These groups are defined by histology, site and degree of surgical resection and are selected to allow meaningful comparison with targeted rates of local control. Target local control rates for these specific treatment groups are established and listed in appendix E based on selected literature (3, 5-6, 9-12, 64,65). A lower limit to the local control rate is given to define a threshold below which the paradigm for treatment described in this protocol is deemed unacceptable. Analysis of local control will be undertaken for a treatment group at each event

Rev 5.2, dated: 6/9/2023 Protocol document date: 6/9/2023

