counted as a local failure, when each treatment group has completed accrual and has been followed for five years, and at intervals specified below. The accrual of patients in five years in the study for all tumor types is projected in Table 12.1.1 below. For the local control analysis, projections for accrual for the specific treatment groups are listed in Table 12.1.2 below. For nonsequential tests, if the actual final accruals are different from the projected accruals, then for Group III RMS or for the Resected or Small ESFT (target 85%), the lower limit to the local control rate is 60%, 70%, 72%, or 73.3%, respectively, for the final accrual of 15, 20, 25, or 30 patients. For the Resected STS (target rate 90%), the lower limit 73.3%, 75%, 76%, or 80%, respectively, for the final accrual of 15, 20, 25, or 30 patients. For the Large ESFT (target rate 55%), the lower limit 33.3%, 35%, 36%, or 40%, respectively, for the final accrual of 15, 20, 25, or 30 patients. A sequential safety-monitoring plan is given in Table 12.1.3 in terms of minimum number for the number of patients locally controlled corresponding to the number of patients accrued within a treatment group during the study, assuming the final accrual is 30 patients in each treatment group. The minimum number is calculated for each of the four treatment groups (Group III RMS, Resected STS, and Resected / Small ESFT, and Large ESFT), respectively. For each of the four treatment groups, when the number of patients accrued during the study reaches 5, 10, 15, 20, 25, or 30, the number of patients with local tumor control will be reviewed and must not be less than the corresponding minimum number (Table 12.1.3). If fewer patients than targeted are controlled locally, then the rate of local control is considered be too low for that treatment group and the study for that treatment group will be stopped for investigating the reasons. At any event counted as a local failure during study, the local control rate for that treatment group will be determined. If the local control rate is lower than targeted, then accrual to that treatment group will be halted and the reasons investigated. If the number of patients accrued is other than 5, 10, 20, 25, or 30, the assistance of the statistician ([name].) may be requested by the PI ([name]) to calculate the new minimum number of patients locally controlled according to the actual number of patients accrued. In the above monitoring scheme, the number of patients locally controlled is counted disregarding the timing (since initiation of radiation therapy) of events (local failures) as this calculation is based on a target rate of local control at 2 years that is identical at 5 years. These target rates are expected estimates of local control and not actual local control rates based directly on historic data. We will use the survival model with competing risk (e.g., patient death) (57) to estimate the rates of local failure and tumor progression (defined in 10.1-10.6) for each tumor group. One-hundred evaluable patients will be required based on the projected accruals in table 12.1.1 below. We expect to enroll a total of 110 patients based on our current accrual to generate 100 evaluable patients for analysis.

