14.0 Data Safety Monitoring Committee

RT-SARC will not be referred to the DSMB at St. Jude Children's Research Hospital because it does not fit any category for DSMB review. The safety in terms of efficacy of local control for this protocol will be monitored by the protocol PI ([name]) according to the plan listed in Table 12.1.2.

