Appendix D

Local control will be estimated for the patient groups indicated below.

Tumor groups are defined as follows:

Rhabdomyosarcoma (RMS)

Group III patients (biopsy or partial resection) followed by definitive radiation

Soft Tissue Sarcoma (STS)

Surgery consisting of a wide local excision (negative or positive margins) followed by radiation

Small or Resected Ewing's Sarcoma Family of Tumors (ESFT)

Surgery consisting of a wide local excision (negative or positive margins) followed by radiation for any primary site of disease

or

Definitive radiation therapy for any small primary site of disease (<8cm in greatest dimension at diagnosis)

Large Ewing's Sarcoma Family of Tumors (ESFT)

Definitive radiation therapy for any large primary site of disease (≥8cm in greatest dimension at diagnosis)

Defined 5 Year Local Control Rates for Evaluable Patient Groups Amend 2.0

	Group III RMS	Resected STS	Resected ESFT or Small ESFT	Large ESFT
Target Local Control Rate	85%	90%	85%	55%
Lower Limit LC Rate	71.4%	75%	66.7%	35%
Projected accrual (n)	28	24	18	12

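### The halting check at each local failure in section 12.1 never defines its comparator; read literally as the target rate, it conflicts with the stopping tables

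*Combined protocol and SAP*

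**What the plan says.** Section 12.1 describes two kinds of monitoring for each treatment group.

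- **Scheduled looks.** At 5, 10, 15, 20, 25 and 30 patients the number locally controlled is compared with a minimum in Table 12.1.3. Table 12.1.5 does the same for second-phase Group III RMS and Resected STS, alone and pooled with the first phase.
- **A check at each failure.** "At any event counted as a local failure during study, the local control rate for that treatment group will be determined". The next sentence gives the consequence: "If the local control rate is lower than targeted, then accrual to that treatment group will be halted and the reasons investigated". No table is named and no minimum number of patients is set.

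The target rates stand in section 12.1 and in the Appendix D row "Target Local Control Rate": 85% (Group III RMS), 90% (Resected STS), 85% (Resected or Small ESFT) and 55% (Large ESFT). The opening of 12.1 gives a different role to another number: "A lower limit to the local control rate is given to define a threshold below which the paradigm for treatment described in this protocol is" judged unacceptable.

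Section 14.0 makes the principal investigator responsible for this monitoring, without referral to the DSMB, "according to the plan listed in Table 12.1.2". That table holds projected accruals and no stopping numbers.

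**The concern.** An observed proportion falls below its true value roughly half the time by chance. A rule that halts whenever the observed rate is under the target, checked at every failure and from the first patient, would therefore often pause a group that is doing what was hoped. It would also overrule the tables, which allow many more failures. If the site instead ignores the sentence, the plan carries a safety rule that nobody applies. In both cases the person monitoring cannot tell from the text which count pauses accrual, and section 14.0 does not help.

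**Working it through.** **1. The plan's own figures.** Section 12.1 gives no error rate for the sequential tables or for the check at each failure. It does give 5% lower limits for the fixed-sample tests. Taking the limit as the smallest r with P(X ≤ r) ≥ 0.05, X ~ Bin(n, target), all four second-phase limits reproduce:

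| Target | n | r | P(X ≤ r) | P(X ≤ r−1) |
|---|---|---|---|---|
| 85% | 35 | 26 | 0.069 | 0.029 |
| 85% | 65 | 50 | 0.055 | 0.028 |
| 90% | 35 | 28 | 0.055 | 0.020 |
| 90% | 65 | 54 | 0.057 | 0.026 |

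**2. Where the literal check and the tables disagree.** The literal check halts at a failure if controlled/enrolled is below the target.

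- A single failure halts an 85% group at any point up to patient 6 (5/6 = 83.3%; 6/7 = 85.7% passes), a 90% group up to patient 9 (8/9 = 88.9%), and the 55% group up to patient 2 (1/2 = 50%). The chances of this at target are 1 − 0.85^6 = 62%, 1 − 0.90^9 = 61% and 1 − 0.55^2 = 70%.
- Group III RMS, 10 patients: 8 controlled is above the minimum of 7, so Table 12.1.3 lets accrual continue; 80% < 85% halts it.
- Group III RMS, 30 patients: Table 12.1.3 continues at 20/30 (10 failures); the literal check halts at 5 failures (25/30 = 83.3%).
- Second phase, 35 patients: Table 12.1.5 continues with 9 failures (RMS, 26/35) or 7 (STS, 28/35). The literal check, if it applies there, halts at 6 (29/35 = 82.9%) or 4 (31/35 = 88.6%).

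**3. Chance of at least one halt when the true rate equals the target.** This is an exact recursion over patients in enrolment order, at the first-phase projected accruals (Table 12.1.2, with and without metastases).

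| Group | n | Outcomes known in enrolment order | Failures within 1 year | Failures within 2 years | All failures after accrual |
|---|---|---|---|---|---|
| Group III RMS | 28 | 80.1% | 69.8% | 56.4% | 41.3% |
| Resected STS | 24 | 72.8% | 64.7% | 54.8% | 43.6% |
| Resected/Small ESFT | 18 | 75.8% | 66.3% | 56.7% | 52.0% |
| Large ESFT | 12 | 84.2% | 72.4% | 57.7% | 47.3% |

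The middle two columns are simulations resting on assumptions the plan does not supply: uniform accrual over five years, failure times uniform over one or two years, and halts counted only while accrual is open. The last column is P(Bin(n, target)/n < target). By then no accrual is left to pause, so it shows only how often the criterion would be met.

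**4. The tables alone, true rate at target.** The text of 12.1 stops below the minimum; the table footnotes stop at or below it. That is a separate inconsistency, so both are shown.

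| Rule | Group | At or below (≤) | Below (<) |
|---|---|---|---|
| Table 12.1.3, to n = 30 | Group III RMS; Resected/Small ESFT | 24.9% | 6.6% |
| | Resected STS | 14.3% | 3.1% |
| | Large ESFT | 3.8% | 1.5% |
| Table 12.1.5, second phase, to n = 35 | Group III RMS | 6.1% | 1.5% |
| | Resected STS | 4.1% | 1.0% |

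**5. The other reading.** Suppose the comparator is the table minimum, interpolated linearly between looks and rounded down (an assumption), with no check before the first tabulated look. The check at each failure, on its own, then halts a group at target as follows: RMS 21.5% (≤) or 6.3% (<); STS 11.7% or 2.8%; Resected/Small ESFT 21.3% or 6.2%; Large ESFT 0.4% or about 0%.

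**The case against.** The strongest reply is that the literal reading is not the intended one. Just before the disputed sentence, 12.1 requires the number controlled to be no lower than the Table 12.1.3 minimum, and then speaks of fewer patients than *targeted*, where the word can only mean that minimum. Just after it, the statistician may be asked for a new minimum when the number accrued is not a tabulated one. Read in sequence, the sentence is a check between looks against a recalculated boundary, which also fits the role that 12.1 gives to the lower limit.

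This stands as a fair reading, but it does not settle the matter. The sentence compares a *rate*, the only target rates in the plan are 85, 90, 85 and 55%, and the opening of 12.1 itself calls those the targeted rates. The recalculation is optional, and no minimums between looks are tabulated.

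Three further replies also stand. A halt here is a pause for investigation, not the end of a group. The 73–84% needs every outcome known in enrolment order; that fits the plan's convention of counting failures without regard to timing, but realistic delay lowers it. And for second-phase Group III RMS and Resected STS, 12.1 holds accrual if either of two table-based plans is triggered and does not mention the check at each failure. The literal figures at n = 35 (82.3% and 77.5%) therefore apply only if that check carries over, which the text does not say.

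**Conclusion.** The concern holds as an undefined halting criterion. Depending on how one word is read, the check pauses a group that meets its target about 0–22% of the time, consistently with the tables, or about 73–84% of the time, against them. The upper range assumes the literal reading, first-phase projected accruals and outcomes known in enrolment order; it becomes about 55–72% under the assumed delays, and the criterion is still met 41–52% of the time if all failures come after accrual.

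A reader might infer that the plan definitely halts sound treatments most of the time and flatly contradicts its own tables. The documents do not support that: the neighbouring sentences allow the table-minimum reading, and under it there is no contradiction. Nor should the contrast be drawn only against the 6% and 4% of Table 12.1.5, since Table 12.1.3 under its footnote already gives 24.9% for RMS and 14.3% for STS.

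This is worth correcting but not critical. The rule governs pauses in accrual only, and section 2.1 says that accrual was almost finished at Amendment 4.0.

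**What to change.** - In 12.1, state that the check at each local failure uses the same sequential boundary as Table 12.1.3 or Table 12.1.5, and have the statistician tabulate in advance the minimum for every number enrolled, in place of the optional request.
- State whether the check applies to second-phase Group III RMS and Resected STS in addition to the two table-based plans.
- In 14.0, replace the reference to Table 12.1.2 with Tables 12.1.3 and 12.1.5.

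The tabulated minimums also need one stopping direction, so the text and the footnotes should be reconciled at the same time.

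The cost is protocol wording and a little statistician time. The one real trade-off is that there will be fewer automatic pauses than under the literal rule.

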The Second Phase Accrual: The original plan of accrual of 110 patients has been completed (September 2007), and additional accrual of patients is planned for this study as the second phase of accrual. The numbers of patients anticipated for the four treatment groups for the second phase accrual are shown in Table 12.1.4. These numbers are estimated based on the accrual of an additional 100 patients with the same distribution of disease (histology, size and use of surgery) as the initial 110 patient cases. For the groups of ESFT-small/resected and ESFT-large, the treatments in the second phase are exactly the same as that in the first phase, so the patients in the second phase will be taking together with those in the first phase for safety monitoring according to the plan in Table 12.1.3. The treatments for the groups of Group III RMS and Resected STS will be changed such that the irradiation margin will be decreased from 2cm to 1.5cm for the Group III RMS, and be decreased from 1.5cm to 1.0cm for the Resected STS. Since the patients in the second phase in these two groups may be at higher risk for local failure than those in the first phase (due to clinical treatment margin reduction), these patients will be monitored separately from, as well as together with, the patients from the first phase. The monitoring plans for these two groups are given in Table 12.1.5. For each group, the accrual of patients will be held if the stopping rule is activated by any one of the two monitoring plans for the aroup.

Table 12.1.4	
The Second Phase Accrual in Groups for Local Control Analysis	

	Group III RMS	Resected STS	Resected ESFT or Small (<8cm) ESFT	Large (≥8cm) ESFT
W & w/o Metastases	35	35	13	12

For Group III RMS or for the Resected or Small ESFT (target 85%), the 5% lower limit for non-sequential tests for the local control rate is 26 (74.3%) or 50 (76.9%), respectively, for the final accrual of 35 or 65 patients. For the Resected STS (target rate 90%), the 5% lower limit is 28 (80.0%) or 54 (83.1%), respectively, for the final accrual of 35 or 65 patients. From the sample sizes of the fixed sample test design, we derived the sequential boundaries in Table 12.1.5 for monitoring the local control rates.

Table 12.1.5

The Second Phase Safety Monitoring Plan: Minimum number of patients locally controlled per patients enrolled in each treatment group*

	Minimum Expected Number of Patients with Local Tumor Control					

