Number of Patients Enrolled	Group I	II RMS	Resecte	ed STS		
in a Treatment Group	2 nd Phase Only	Two Phases Together	2 nd Phase Only	Two Phases Together		
5	2		2			
10	5		6			
15	9		10			
20	12		14			
25	16		18			
30	20		22			
35	25		27			
40		28		31		
45		32		35		
50		36		39		
55		40		44		
60		44		48		
65		49		53		

*For the second phase accrual for each of the two treatment groups, the local controls will be monitored simultaneously in two ways: 1) alone: when the number of patients accrued from the second phase accrual reaches 5, 10, 15, 20, 25, or 35, if the number of patients locally controlled is equal to or less than the corresponding minimum number, then the rate of local control is considered be too low for that treatment group and the study for that group will be stopped for investigating reasons; 2) together with patients accrued in the first phase: during the second phase accrual, if the number of all patients accrued so far from the two phases reaches 40, 45, 50, 55, 60, or 65 and if the number of patients locally controlled is equal to or less than the corresponding minimum number, then the rate of local control is considered be too low for that study for that group will be stopped for investigating minimum number, then the rate of local control is considered be too and if the number of patients locally controlled is equal to or less than the corresponding minimum number, then the rate of local control is considered be too low for that treatment group and the study for that group will be stopped for investigating reasons.

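### Follow-up for local control can end at metastatic-only progression, Table 12.1.3 carries two stopping inequalities, and the interim looks count patients before their local status is known

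*Combined protocol and SAP*

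**What the plan says.** **Follow-up.** Section 13.2.2 makes any off-study criterion in 13.3 a ground for removal from follow-up, and 13.3.2 lists progression of local or of metastatic disease. Section 10.5 classifies metastatic progression separately from local failure. Section 2.5 extends follow-up to 10+ years for everyone enrolled, and objective 1.1.4 asks for local control beyond five years. Section 12.1 estimates local failure with a competing-risk model and names patient death only as an example of a competing event.

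**Table 12.1.3.** The body of 12.1 stops a group when fewer patients are controlled than the tabulated minimum. The table's footnote also stops it when the count equals the minimum. Section 12.1 keeps both ESFT groups on this table in the second phase. Table 12.1.5 has only the footnote form.

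**Interim looks.** Looks are triggered by enrolment, in the second phase "when the number of patients accrued from the second phase accrual reaches 5, 10, 15, 20, 25, or 35". At each, "the number of patients locally controlled is counted disregarding the timing (since initiation of radiation therapy) of events (local failures"). The reason given is a "target rate of local control at 2 years that is identical at 5 years". On the boundaries, the plan says: "From the sample sizes of the fixed sample test design, we derived the sequential boundaries in Table 12.1.5". A further rule applies at each local failure: "If the local control rate is lower than targeted, then accrual to that treatment group will be halted". Section 12.1 says "Target local control rates for these specific treatment groups are established and listed in appendix E"; the table of targets stands in Appendix D.

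**The concern.** In all three places a patient can count as locally controlled, or a group can pass a look, without the data that would justify it.

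- **Follow-up.** A patient who leaves at metastatic progression can fail locally later without the failure being recorded. This touches the primary endpoint and stays live for as long as follow-up runs.
- **Inequality.** Two people can apply Table 12.1.3 to the same data and decide differently. With 7 of 10 Group III RMS patients controlled, the text continues and the footnote stops.
- **Looks.** Equal 2-year and 5-year targets justify ignoring time for patients past two years. They say nothing about patients enrolled last month, who count as controlled. The second-phase rule exists because these patients "may be at higher risk for local failure than those in the first phase", so lost sensitivity matters there.

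**Working it through.** **1. The plan's own figures.** Take the smallest k with P(X ≤ k) ≥ 0.05 for X ~ Bin(n, target). Target 85% gives 26 (n = 35) and 50 (n = 65); target 90% gives 28 and 54. All four agree with the non-sequential limits in 12.1. They are binomial limits on completed outcomes.

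**2. Off-study rule, count-based tests.** If a share h of local failures goes unrecorded, the counted rate is 1 − (1 − p)(1 − h), which is never below p. With h assumed at 0/10/20/30%, the chance of a count at or below the limit is:

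| True control | Limit | h = 0 | 10% | 20% | 30% |
|---|---|---|---|---|---|
| RMS 71.4% | 26 of 35 | 71% | 57% | 41% | 26% |
| RMS 71.4% | 50 of 65 | 87% | 73% | 53% | 31% |
| STS 75% | 28 of 35 | 81% | 70% | 57% | 42% |

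Break-even against Appendix D: 28 × (0.85 − 0.714) = 3.8 missed RMS failures, or 12 × (0.55 − 0.35) = 2.4 missed large-ESFT failures, span the gap from lower limit to target.

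**3. Off-study rule, competing-risk estimate.** Assumed annual hazards: local failure 0.06 before metastasis, metastasis 0.10, death 0.01 before and 0.6 after.

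- Censoring at metastasis, the 5-year control estimate tends to 1 − (0.06/0.07)(1 − e^(−0.35)) = 74.7%.
- True control, counting local failure at any time, is 77.5% if the local-failure hazard stays 0.06 after metastasis. The estimate is then too low.
- True control is 71.9% if that hazard rises to 0.24. The estimate is then too high.
- If the estimand is local failure as first event, control is 1 − (0.06/0.17)(1 − e^(−0.85)) = 79.8%.

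The sign depends on handling and on event rates after metastasis, and the documents give neither.

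**4. Table 12.1.3, two inequalities.** Exact binomial recursion over the looks, mature outcomes, truth at target:

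| Group | Stop if below | Stop if equal or below |
|---|---|---|
| Group III RMS; resected/small ESFT (85%) | 6.6% | 24.9% |
| Resected STS (90%) | 3.1% | 14.3% |
| Large ESFT (55%), only if look 30 is reached | 1.5% | 3.8% |

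For resected/small ESFT the footnote rule has accumulated 24.1% by look 10 and 24.8% by look 15. With 18 patients projected in phase 1 (Table 12.1.2), looks 20 to 30 add about 0.2 points. If phase 1 held about 14 (13 × 110/100, from Table 12.1.4), the later looks add about 0.8. Large ESFT is projected at 12 + 12 = 24; through look 20 the figures are 0.1% and 0.9%.

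**5. Interim looks.** At 28/5 = 5.6 RMS patients a year, evenly spaced, two years spans 11.2 enrolments. So 0 of 5, 0 of 10, 3 of 15, 8 of 20, 13 of 25 and 18 of 30 patients have two years of follow-up at their look.

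The second-phase rule alone was simulated (15,000-20,000 runs per setting). It stops when the count is at or below the Table 12.1.5 entry, at all seven rows; the footnote's list omits 30, though the table has that row. Assumptions: Poisson accrual of 35 patients at 7 (35/5), 5.6 (RMS) or 4.8 (STS, 24/5), 3.5 (35/10) or 2.33 (35/15) per year; all failures within two years, median 0.5 to 1.25 years. Mature figures are exact.

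| True control | Mature | As written |
|---|---|---|
| RMS 71.4% | 61% | 19-49% |
| RMS 85% (target) | 6.1% | 0.4-2.6% |
| STS 75% | 72% | 33-62% |
| STS 90% (target) | 4.1% | 0.4-2.4% |

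**6. Per-failure trigger.** Read against the target, one failure among the first six RMS patients halts accrual (5/6 = 83.3% < 85%). It halts 92-99% of RMS groups at 71.4% and 96-99% of STS groups at 75%, but also 50-77% of RMS and 51-74% of STS groups truly at target. Read against the interpolated table minimum, it adds about 0.5-3 points to the looks.

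**The case against.** Three stronger readings are tempting, and the documents do not support them.

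- **Unrecorded failures must flatter the primary result.** The primary estimate is a competing-risk model, not a count. A patient leaving under 13.3.2 might ordinarily be censored, and step 3 shows bias in either direction. The break-even and the h table apply to the count-based tests only. It is also fair that off-study criteria usually qualify a general follow-up statement, and that 13.1 says patients may be taken off. The rule permits loss of follow-up; it does not make it certain.
- **24.9% false stopping is a current exposure.** RMS and STS moved to Table 12.1.5 in phase 2, and phase-1 accrual finished in September 2007. For ESFT, little remains at target.
- **The monitoring is simply insensitive.** Other rules run alongside the looks. With the trigger read against the target, the scheme over-triggers. With the pooled rule added (30 mature phase-1 patients at target, assumed), stopping rises only to 23-52% (RMS at 71.4%) and 38-65% (STS at 75%). The scheme is uncalibrated, which is a different criticism.

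It also stands that 12.1 discloses the simplification, that it plans an analysis after five years of follow-up, that a stop means a halt to investigate, and that section 2 describes accrual as nearly complete at Amendment 4.0. That the boundaries presume completed outcomes is an inference from the fixed-sample derivation.

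**Conclusion.** The concern holds in three parts of unequal weight.

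1. **Off-study rule.** This matters most while follow-up continues. The conflict between 13.2.2/13.3.2 and section 2.5 with objective 1.1.4 is in the text. The effect is upward in the counts and of unknown direction in the competing-risk estimate; its size cannot be computed from the documents.
2. **Inequality.** The conflict is certain and needs no assumption about pace or timing. Its effect falls mainly on looks already past; for resected/small ESFT the remaining looks add under one point at target.
3. **Interim looks.** The direction is certain for the count-based rule alone: immature counts can only be too high. The size rests on assumed pace and failure timing. The per-failure trigger does not repair the loss in a calibrated way, because its threshold is ambiguous and the two readings behave oppositely. The five-year competing-risk estimate is not affected by this part.

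**What to change.** 1. Reconcile 13.2.2/13.3.2 with section 2.5 so that chart-based local and vital status is still collected after metastatic-only progression. State whether the estimand is local failure at any time or as first event, and how these patients enter the model. Where status is missing, report a range from none failed to all failed. Cost: amendment wording and chart review.
2. Reconcile the text and footnote of Table 12.1.3 to one inequality, and report which was applied at past looks. Cost: wording only.
3. Apply each boundary to the first n patients in enrolment order once each has two years of local follow-up, has failed locally or has died. State how deaths without local failure count, which threshold the per-failure rule uses, and its operating characteristics. Cost: each look comes about two years later, after roughly 5 to 14 more enrolments (2 × 2.33 to 2 × 7). This restores the mature rates in step 5. In simulation it still stops more poor groups before the 35th enrolment than the rule as written: RMS at 71.4%, 32-43% against 7-31%; STS at 75%, 42-57% against 17-47%.

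If accrual is complete, replace item 3 with one report of the 35- and 65-patient boundaries on mature data, next to the non-sequential limits already in 12.1. Only item 1 then changes ongoing conduct.

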
Table 12.1.1 Projected Accruals

	RMS	STS	ESFT
W/o Metastases	18	26	26
W & w/o Metastases	29	26	37

Table 12.1.2 Accrual in Groups for Local Control Analysis

	Group III RMS	Resected STS	Resected ESFT or Small (<8cm) ESFT	Large (≥8cm) ESFT
W/o Metastases	17	24	15	3
W & w/o Metastases	28	24	18	12

Table 12.1.3

Safety Monitoring Plan: Minimum number of patients locally controlled per patients enrolled in each treatment group*

	Minimum Expected Number of Patients with Local Tumor Control								
Number of			Resected ESFT						
Patients Enrolled	Group III	Resected	or						
in a Treatment	RMS	STS	Small (<8cm)	Large (≥8cm) ESFT					
Group			ESFT						
5	3	3	3						
10	7	7	7	1					
15	10	11	10	3					
20	13	15	13	4					
25	16	19	16	7					
30	19	22	19	11					

*For each of the three treatment groups, when the number of patients accrued during the study reaches 5, 10, 15, 20, 25, or 30, if the number of patients locally controlled is equal to or less than the corresponding minimum number, then the rate of local control is considered be too low for that treatment group and the study for that group will be stopped for investigating reasons.

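### Table 12.1.3 assumes 30 patients per group, so its remaining looks have little power to stop either Ewing group in the second phase

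*Combined protocol and SAP*

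**What the plan says.** Section 12.1, under the second-phase accrual, gives new boundaries (Table 12.1.5) only to Group III RMS and resected STS. The Ewing treatment is unchanged, so second-phase Ewing patients are pooled with the first-phase ones "for safety monitoring according to the plan in Table 12.1.3". That table was calculated "assuming the final accrual is 30 patients in each treatment group".

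The plan's lower limits are meant to "define a threshold below which the paradigm for treatment described in this protocol is deemed unacceptable". Appendix D, in the table headed "Defined 5 Year Local Control Rates for Evaluable Patient Groups", sets targets of 85% (resected/small ESFT) and 55% (large ESFT), with lower limits of 66.7% and 35%. Section 12.1 also gives limits by final accrual of 15, 20, 25 or 30. For the 85% groups "the lower limit to the local control rate is 60%, 70%, 72%, or 73.3%, respectively"; for large ESFT they are 33.3%, 35%, 36% and 40%.

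Two further statements in section 12.1 matter. The text stops a group only when the controlled count is below the tabulated number, whereas the footnote to Table 12.1.3 stops it at or below that number. Separately, at each local failure the group's rate is to be worked out, and accrual halts if it is under target.

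**The concern.** A boundary table built for 30 patients loses its last looks when fewer are enrolled. A table that uses up most of its stopping probability early also has little left for a group that has already passed those looks. Both seem to apply here. The looks still ahead on projected accrual are 3 of 15 and 4 of 20 (20% and 20%) for large ESFT, and 13 of 20, 16 of 25 and 19 of 30 (65%, 64% and 63.3%) for resected/small ESFT. Each is below the plan's own lower limit at that number of patients.

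At stake is whether the named second-phase rule could act on a control rate that the plan itself regards as unacceptable. Section 14 leaves this monitoring to the principal investigator without DSMB review, and cites Table 12.1.2, an accrual table, as the plan.

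**Working it through.** **Plan's own figures first.** The stated 5% limits are the exact binomial 5% quantiles. A target of 85% gives 26 of 35 and 50 of 65; a target of 90% gives 28 and 54. All four match. At n=30 the quantile is 22 for 85% (73.3%) and 12 for 55% (40%), also as printed. At n=25 for large ESFT the exact quantile is 10, where the plan's 36% corresponds to 9.

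**Final boundary against limit.** In Table 12.1.5 the pairs are 25/26, 49/50, 27/28 and 53/54, always one below. In Table 12.1.3 large ESFT fits (11/12); resected/small does not (19/22, three below).

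**Accrual.** Adding Tables 12.1.2 and 12.1.4 gives large 12+12=24 and resected/small 18+13=31. Actual first-phase counts are not given. Table 12.1.4 assumes 100 patients with the same mix as the first 110, so scaling back (an assumption) gives 12×1.1≈13 and 13×1.1≈14, and totals of about 25 and 27. The large look at 30 is missed either way. The look at 25 is missed on the direct sum and only just reached on the scaled one.

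**Method.** Exact sequential binomial with true rate p, timing ignored as the plan does. Let f_j(x) be the probability of arriving at look j unstopped with x controlled. With m patients added since the last look, f_j(x) = Σ_y f_{j−1}(y)·C(m, x−y)·p^(x−y)·(1−p)^(m−x+y), over unstopped y. The probability of stopping at look j is the sum of f_j(x) for x ≤ b (footnote) or x ≤ b−1 (text). For example, large ESFT at n=10 with b=1 and p=0.35: under ≤, 0.65^10 + 10(0.35)(0.65^9) = 0.0135+0.0725 = 0.0860; under <, 0.0135.

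**Cumulative stopping, large ESFT (boundaries 1, 3, 4, 7, 11)**

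| by n | 35%, < | 35%, ≤ | 55%, < | 55%, ≤ |
|---|---|---|---|---|
| 10 | .0135 | .0860 | .0003 | .0045 |
| 15 | .0649 | .1905 | .0013 | .0089 |
| 20 | .0775 | .2097 | .0014 | .0092 |
| 25 | .1889 | .3493 | .0026 | .0127 |
| 30 | .5108 | .6633 | .0145 | .0381 |

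Given that n=10 was passed, the looks at 15 and 20 stop (.0775−.0135)/(1−.0135)=6.5% under <, and (.2097−.0860)/(1−.0860)=13.5% under ≤. If 5 or more of 12 first-phase patients are and stay controlled, those two looks cannot be triggered.

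**Cumulative stopping, resected/small ESFT (boundaries 3, 7, 10, 13, 16, 19)**

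| by n | 66.7%, < | 66.7%, ≤ | 85%, < | 85%, ≤ |
|---|---|---|---|---|
| 5 | .2094 | .5384 | .0266 | .1648 |
| 10 | .4615 | .7435 | .0608 | .2411 |
| 15 | .5206 | .7793 | .0646 | .2476 |
| 20 | .5522 | .7969 | .0655 | .2490 |
| 25 | .5722 | .8075 | .0657 | .2493 |
| 30 | .5862 | .8146 | .0658 | .2494 |

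By n=15 the column has spent .5206/.5862=89% (<) or .7793/.8146=96% (≤) of its stopping probability at 66.7%. Given that n=15 was passed, the looks at 20, 25 and 30 stop (.5862−.5206)/(1−.5206)=14% or (.8146−.7793)/(1−.7793)=16%. If only n=10 has been passed and accrual ends near 27, the looks at 15, 20 and 25 stop (.5722−.4615)/(1−.4615)=21% or (.8075−.7435)/(1−.7435)=25%.

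**Illustrative replacements under ≤, with the last boundary one below the 5% quantile (9 of 24; 23 of 31)**

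- Large, 1/10, 3/15, 5/20, 8/24: 53.7% stopping at 35%, 3.1% false stops at 55%.
- Resected/small, 2/5, 5/10, 9/15, 12/20, 16/25, 22/31: 77.9% at 66.7%, 6.3% at 85%. The printed column under the same rule gives 81.5% and 24.9%.
- If only the looks after n=15 change for resected/small, stopping at 66.7% given that n=15 was passed is 44% to 57%, depending on which inequality governed the earlier looks.

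**The case against.** The strongest reply is that Table 12.1.3 does not stand alone. The rule applied at each local failure covers every group and is not withdrawn for the second phase. Read literally it is far more sensitive: in an 85% group any failure among the first six patients gives at most 5/6=83.3% and halts accrual, which happens with probability 1−0.85^6=62% even at target. A reader might infer that the table is the only protection for Ewing patients, and the documents do not support that. What stands is that the two rules cannot both operate as written, and that Table 12.1.3 is the one named for second-phase Ewing monitoring.

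A reader might also infer that the resected/small column cannot stop a poor group. Over the whole table it can: 59% at 66.7% with 6.6% false stops under <, or 81% with 25% under ≤. On the footnote's reading its fault is excess early stopping. The 14% to 16% depends on conditioning on the n=15 look; the looks at 20, 25 and 30 taken alone would stop 41% (<) to 59% (≤). Late first-phase failures count too and would raise the conditional figure.

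Further points have some force. The totals are projections. The statistician may be asked for minimum numbers at other accruals, though this is optional. Boundaries below a fixed-sample limit are normal at interim looks. Large ESFT is limited by its size: even a single 5% test at n=24 detects 35% only 53% of the time. The background describes accrual as nearly complete, so little may be left to monitor, although section 2.5 still accrues to 210.

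**Conclusion.** The concern holds in a bounded form. For large ESFT it is firm: at 35% control the chance of stopping is 8% to 21% by n=20, or 19% to 35% if n=25 is reached, against 51% to 66% had the assumed 30 been enrolled. For resected/small ESFT it is conditional: a group that has passed n=15 has a 14% to 16% chance of being stopped later at 66.7%, or 21% to 25% by n=25 if the look at 15 is still to come.

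These figures rest on projected accrual, immediately known outcomes, and treating the lower limit as a true rate. They say nothing about actual Ewing control: section 2.1 reports 95% at 2 years (unpublished, not split by group), so it would be wrong to infer that a poor result was missed. Equally, the absence of a stop under these looks is weak evidence that control is acceptable.

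**What to change.** Re-derive the remaining second-phase boundaries for both Ewing groups at actual first-phase counts plus planned second-phase accrual. Use the Table 12.1.5 approach, with the final boundary one below the 5% limit at the true total. State one direction of the inequality in both text and footnote, and report false-stop and stopping probabilities under that same direction. Reconcile the table with the rule applied at each local failure, saying which governs. The columns at 24 and 31 shown above are illustrations and should be replaced once the real counts are entered.

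The cost is recalculation of two columns, with no extra patients. For large ESFT, false stops under ≤ rise from 0.9% (printed, by n=20) to 3.1% (by n=24), about two percentage points. For resected/small under ≤, the illustrative column gives up about four points of stopping at 66.7% (81.5% to 77.9%) and cuts false stops from 25% to 6.3%. Most of that change falls in early looks that, on projected accrual, are already past.
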